10.2.1 Required Laboratory Parameters for Treatment

A new dose of therapy may be initiated provided that the patient meets the following criteria within 72 hours of treatment:

- ANC \geq 1,000/ μ L

- Platelets > 75,000/ μ L
- All grade \geq 2 non-hematologic adverse events (except for fatigue, nausea and vomiting, or laboratory values that are not clinically significant) must have resolved to CTCAE grade \leq 1
- No evidence of infection/necrosis or local complications in the injection site.

10.3 – Tumor and blood samples for correlative/companion studies

All patients enrolled on this study will undergo paired biopsies/blood samples for research purposes (correlative/companion studies)

Metastatic/inoperable, locally advanced cohort:

Blood samples for research purposes will be obtained at week 1, 4, 7, 13, 19, 22 and at the date of the off study visit (\pm 7 days). This is detailed in Table 6 (Study calendar).

Biopsies for research purposes will be done at baseline (within 30 days of the first dose of talimogene laherparepvec and/or pembrolizumab) and at Week 8 in all patients enrolled in this study where feasible. Biopsy of a distant site of disease at each biopsy timepoint will be obtained. A site not intended to be injected is preferred for biopsy where feasible. Up to 6 cores from each tumor biopsy site should be taken where feasible and safe to do so. A goal of 6 cores should be obtained with a minimum of one formalin-fixed, one fresh and one flash frozen in liquid nitrogen. Biopsy procedures will otherwise be performed in accordance with institutional guidelines and the biopsy guideline outlined in Appendix F. An optional biopsy of a distant site of disease will be offered to all patients at the time of progression.

Neoadjuvant cohort:

Blood samples for research purposes will be obtained at week 1, 4, and week 6 and 12 (where applicable) prior to surgical resection. For patients receiving additional cycles of treatment, additional blood samples will be drawn prior to each cycle.

Mandatory biopsies for research purposes will be done at baseline (within 30 days of the first dose of talimogene laherparepvec and/or pembrolizumab) and at Week 4 prior to the administration of study therapy. For patients receiving additional cycles of treatment, additional core biopsies may be obtained prior to each additional treatment (ie. week 7 and week 10, etc.)

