11.4.1 Talimogene laherparepvec

Dose reductions – talimogene laherparepvec

Dose reductions with regards to changes in the concentrations of talimogene laherparepvec are not permitted. However, patients may require a reduction in the volume injected due to a disease response (defined in dosing section) or due to local toxicity at the injection site.

Dose delays and rules for withholding/restarting treatment – talimogene laherparepvec

If a subject experiences any of the following treatment-related toxicities, talimogene laherparepvec administration should be delayed until the toxicity has resolved to at least CTCAE grade 1 or baseline:

- grade 2 or greater immune-mediated adverse events, with the exception of vitiligo
- grade 2 or greater allergic reactions
- any other grade 3 or greater hematologic or non-hematologic toxicity

Upon restarting study therapy, the patient's treatment schedule should be reset from the date that therapy is reinitiated as to maintain appropriate treatment windows between therapy administrations.

If the subject requires corticosteroid dosing of >10 mg prednisone daily (or equivalent) and/or other immunosuppressive medication for related toxicities talimogene laherparepvec dosing must be held until the corticosteroid dose has decreased to ≤10 mg prednisone daily (or equivalent) and the administration of the other immunosuppressive medication has discontinued.

Subjects who are receiving talimogene laherparepvec may not receive systemic intravenous or oral antiherpetic drugs (e.g., acyclovir, valacyclovir, famciclovir), but may receive a topically administered antiherpetic drug more than 20 cm from a talimogene laherparepvec injection site. Dosing should be permanently discontinued if, in the opinion of the investigator, the subject develops clinical evidence of any systemic herpes infection (such as encephalitis or disseminated infection).

Dosing of talimogene laherparepvec could also be delayed for active herpetic cutaneous or mucosal lesions, herpes labialis, antiviral therapy, or active dermatoses in the region of the injected tumors.

Permanent discontinuation – talimogene laherparepvec

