11.4.2 Pembrolizumab

Dose reductions – Pembrolizumab

Dose reductions of pembrolizumab are not permitted.

Dose Modification and Toxicity Management

Adverse events (both non-serious and serious) associated with pembrolizumab exposure, including coadministration with additional compounds, may represent an immunologic etiology. These adverse events may occur shortly after the first dose or several months after the last dose of pembrolizumab/combination treatment and may affect more than one body system simultaneously. Pembrolizumab must be withheld for drug-related toxicities and severe or life-threatening AEs as per table 10 below. See Section 5.6 for supportive care guidelines, including use of corticosteroids.

Attribution of Toxicity:

When study interventions are administered in combination, attribution of an adverse event to a single component is likely to be difficult. Therefore, while the investigator may attribute

a toxicity event to the combination, to talimogene laherparepvec alone or to pembrolizumab alone], for adverse events listed in Table 10, both interventions must be held according to the criteria in Table 10 Dose Modification and Toxicity Management Guidelines for Immune-Related Adverse Events Associated with Pembrolizumab.

Holding Study Interventions:

When study interventions are administered in combination, if the AE is considered immune-related, both interventions should be held according to recommended dose modifications.

Restarting Study Interventions:

Participants may not have any dose modifications (no change in dose or schedule) of pembrolizumab in this study, as described in Table 10.

- If the toxicity does not resolve or the criteria for resuming treatment are not met, the participant must be discontinued from all study interventions.
- If the toxicities do resolve and conditions are aligned with what is defined in Table 10, the combination of talimogene laherparepvec and pembrolizumab may be restarted at the discretion of the investigator.[In these cases where the toxicity is attributed to the combination or to talimogene laherparepvec alone, re-initiation of pembrolizumab as a monotherapy may be considered at the principal investigator's discretion

Table 10. Dose modification and toxicity management guidelines for immune-related AEs associated with pembrolizumab monotherapy and IO combinations

General instructions:				

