Hypophysitis	Grade 2	Withhold	
 Administer corticosteroids and initiate hormonal replacements as clinically indicated. 	
 Monitor for signs and symptoms of hypophysitis (including hypopituitarism and adrenal insufficiency)
	Grade 3 or 4	Withhold or permanently discontinue ^d		
Hyperthyroidism	Grade 2	Continue	
 Treat with non-selective beta-blockers (e.g. propranolol) or thionamides as appropriate 	
 Monitor for signs and symptoms of thyroid disorders.
	Grade 3 or 4	Withhold or Permanently discontinue ^d		
Hypothyroidism	Grade 2-4	Continue	
 Initiate thyroid replacement hormones (e.g. levothyroxine or liothyronine) per standard of care 	
 Monitor for signs and symptoms of thyroid disorders.
Nephritis: grading according to increased creatinine or acute kidney injury	Grade 2	Withhold	
 Administer corticosteroids (prednisone 1- to 2mg/kg or equivalent) followed by taper. 	
 Monitor changes of renal function
	Grade 3 or 4	Permanently discontinue		
Neurological Toxicities	Grade 2	Withhold	
 Based on severity of AE administer corticosteroids 	
 Ensure adequate evaluation to confirm etiology and/or exclude other causes
	Grade 3 or 4	Permanently discontinue		
Myocarditis	Grade 1	Withhold		
 Ensure adequate evaluation to confirm etiology and/or exclude other causes

	Grade 2, 3, or 4	Permanently discontinue	
 Based on severity of AE administer corticosteroids 	
Exfoliative Dermatologic Conditions	Suspected SJS, TEN, or DRESS	Withhold	
 Based on severity of AE administer corticosteroids 	
 Ensure adequate evaluation to confirm etiology or exclude other causes
	Confirmed SJS, TEN, or DRESS	Permanently discontinue		
All Other immune-related AEs	Grade 3, or intolerable/persistent Grade 2	Withhold	
 Based on severity of AE administer corticosteroids 	
 Ensure adequate evaluation to confirm etiology or exclude other causes
	Grade 4 or recurrent Grade 3	Permanently discontinue		

NOTES:

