- Therapy with pembrolizumab can be continued while treatment for the thyroid disorder is instituted.
- In hyperthyroidism, non-selective beta-blockers (e.g. propranolol) are suggested as initial therapy.
- In hypothyroidism, thyroid hormone replacement therapy, with levothyroxine or liothyronine, is indicated per standard of care.
- Consultation with an endocrinologist may be considered.

Grade 3 hyperthyroidism events:

- Hold pembrolizumab.
- Rule out infection and sepsis with appropriate cultures and imaging.
- Treat with an initial dose of methylprednisolone 1 to 2 mg/kg intravenously followed by oral prednisone 1 to 2 mg/kg per day. When symptoms improve to Grade 1 or less, steroid taper should be started and continued over no less than 4 weeks. Replacement of appropriate hormones may be required as the steroid dose is tapered.
- Permanently discontinue for inability to reduce corticosteroid dose to 10 mg or less of prednisone or equivalent per day within 12 weeks.

Grade 4 events:

- Discontinue pembrolizumab.
- Manage as per Grade 3

A2.4 Hematologic

All attempts should be made to rule out other causes such as metastases, sepsis and/or infection. Relevant diagnostic studies such as peripheral blood smear, reticulocyte count, LDH, haptoglobin, bone marrow biopsy or Coomb's test, etc., should be considered to confirm the diagnosis.

Course of Action

Grade 2 events:

- Hold pembrolizumab
- Prednisone 1-2 mg/kg daily may be indicated
- Consider Hematology consultation.
- Permanently discontinue for inability to reduce corticosteroid dose to 10 mg or less of prednisone or equivalent per day within 12 weeks.

Grade 3 events:

- Hematology consultation.
- Hold pembrolizumab Discontinuation should be considered as per specific protocol guidance.
- Treat with methylprednisolone 125 mg iv or prednisone 1-2 mg/kg p.o. (or equivalent) as appropriate

- Permanently discontinue for inability to reduce corticosteroid dose to 10 mg or less of prednisone or equivalent per day within 12 weeks.

Grade 4 events:

- Hematology consultation
- Discontinue pembrolizumab for all solid tumor indications; refer to protocol for hematologic malignancies.
- Treat with methylprednisolone

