3.5 Hepatic

Course of Action

Grade 2 events:

- Hold pembrolizumab
- Monitor liver function tests more frequently until returned to baseline values (consider weekly).
- Treat with 0.5-1 mg/kg/day methylprednisolone or oral equivalent and when LFT returns
- to grade 1 or baseline, taper steroids over at least 1 month, consider prophylactic antibiotics for opportunistic infections, and resume pembrolizumab per protocol
- Permanently discontinue for inability to reduce corticosteroid dose to 10 mg or less of prednisone or equivalent per day within 12 weeks.
- Permanently discontinue pembrolizumab for patients with liver metastasis who begin treatment with Grade 2 elevation of AST or ALT, and AST or ALT increases $\geq 50\%$ relative to baseline and lasts ≥ 1 week.

Grade 3 events:

- Discontinue pembrolizumab when AST or ALT >5.0 times ULN and/or total bilirubin >3.0 times ULN.
- Consider appropriate consultation and liver biopsy to establish etiology of hepatic injury, if necessary
- Treat with high-dose intravenous glucocorticosteroids for 24 to 48 hours.
 - When symptoms improve to Grade 1 or less, a steroid taper with dexamethasone 4 mg every 4 hours or prednisone at 1 to 2 mg/kg should be started and continued over no less than 4 weeks.
- If serum transaminase levels do not decrease 48 hours after initiation of systemic steroids, oral mycophenolate mofetil 500 mg every 12 hours may be given. Infliximab is not recommended due to its potential for hepatotoxicity.
- Several courses of steroid tapering may be necessary as symptoms may worsen when the steroid dose is decreased.
- Permanently discontinue for inability to reduce corticosteroid dose to 10 mg or less of prednisone or equivalent per day within 12 weeks.

Grade 4 events:

- Permanently discontinue pembrolizumab
- Manage patient as per Grade 3 above

A2.6 Neurologic

All attempts should be made to rule out other causes such as metastatic disease, other medications or infectious causes.

Course of Action

Grade 2 events:

- Moderate (Grade 2) – consider withholding pembrolizumab.
- Consider treatment with prednisone 1-2 mg/kg p.o. daily as appropriate
- Consider Neurology consultation. Consider biopsy for confirmation of diagnosis.
- Permanently discontinue for inability to reduce corticosteroid dose to 10 mg or less of prednisone or equivalent per day within 12 weeks.

Grade 3 and 4 events:

- Discontinue pembrolizumab
- Obtain neurology consultation. Consider biopsy for confirmation of diagnosis

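### Sections 10.2.1 and 11.4.1 can bar dosing for thyroid and other endocrine immune events that Table 10 and Appendix A tell the investigator to treat through, so the rules need reconciling

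*Combined protocol and SAP*

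**What the plan says.** **Section 10.2.1** sets a condition on dosing in general, naming neither drug: "A new dose of therapy may be initiated provided that the patient meets the following criteria within 72 hours of treatment". Grade 2 or higher non-hematologic events (except fatigue, nausea and vomiting, or "laboratory values that are not clinically significant) must have resolved to CTCAE grade" 1 or less. There is no endocrine exception and no reference to Table 10.

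**Section 11.4.1** lists among the treatment-related triggers for a T-VEC delay "grade 2 or greater immune-mediated adverse events, with the exception of vitiligo". In that case "talimogene laherparepvec administration should be delayed until the toxicity has resolved to at least CTCAE grade 1 or baseline".

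**Section 11.4.2** says that, whichever drug is blamed, for events listed in Table 10 "both interventions must be held according to the criteria in Table 10".

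**Table 10** gives Continue for grade 2-4 hypothyroidism, with the management note "Initiate thyroid replacement hormones (e.g. levothyroxine or liothyronine) per standard of care", and Continue for grade 2 hyperthyroidism. Footnote d covers grade 3-4 hyperthyroidism, grade 3-4 hypophysitis, and new type 1 diabetes or severe hyperglycemia. It lets pembrolizumab resume once control is achieved or the event is grade 2 or less.

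**Appendix A, A2.3 Endocrine**, for grade 2 thyroid events and grade 3-4 hypothyroidism: "Therapy with pembrolizumab can be continued while treatment for the thyroid disorder is instituted".

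**Section 11.1.1** counts a related event as a treatment-related toxicity event if it leads to discontinuation or to a delay of more than 9 weeks. It takes the patient off the related drug after such a delay.

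**The concern.** An investigator with a patient who has grade 2 hypothyroidism on hormone replacement has two sets of instructions. Table 10 and Appendix A say to carry on. Section 10.2.1 says not to dose, and section 11.4.1 says to delay T-VEC if the event is related. Two investigators could treat the same patient differently and both be following the protocol.

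The choice affects exposure to both drugs and who is discontinued. It also affects the toxicity count, because a related hold of more than 9 weeks is a counted event. Hypothyroidism is the natural test case. Section 11.3.1 reports it in 34 of 411 melanoma patients on pembrolizumab, all but two of them on long-term replacement.

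**Working it through.** **Step 1. The rules side by side** (related event, no other toxicity)

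| Event | Table 10 (both drugs, per 11.4.2) | Appendix A (pembrolizumab) | 10.2.1 (any new dose) | 11.4.1 (T-VEC) |
|---|---|---|---|---|
| Hypothyroidism, grade 2-4 | Continue | Continue | No dose until grade 1 or less, unless only a laboratory value that is not clinically significant | Delay until grade 1 or baseline |
| Hyperthyroidism, grade 2 | Continue | Continue | As above | As above |
| Events under footnote d, improved to grade 2 | Pembrolizumab may resume | – | As above | As above |

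In each row the first column permits dosing and at least one of the last two does not.

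**Step 2. Table 10 against Appendix A.** The two agree on the thyroid rows above and differ in strictness elsewhere:
- Neurologic, grade 2: withhold, against "consider withholding pembrolizumab" in A2.6.
- Hypophysitis and hyperthyroidism, grade 4: withhold or permanently discontinue, against discontinue.
- Other immune events: withhold at grade 3 or at intolerable or persistent grade 2, against withhold at any grade 2 or at grade 1 that does not improve.

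In each of these, some action satisfies both texts.

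**Step 3. Reproducing the plan's stopping probabilities.** Section 14.1 gives the boundary as 2/4, 3/8, 4/14 or 5/20 and states stopping probabilities of about 10% and 79% at true event rates of 10% and 30%. I used an exact binomial recursion over patients 1 to 20. It stops at the first n with at least 2 events (n ≤ 4), 3 (n ≤ 8), 4 (n ≤ 14) or 5 (n ≤ 20).
- Counting the look at patient 20: 10.4% and 81.6%.
- Stopping only before patient 20: 9.9% and 78.8%, which matches the stated pair.

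**Step 4. Illustration of size.** Inputs: h = 34/411 = 0.0827 (section 11.3.1, all grades), and b, the rate of all other toxicity events. The assumed share s is the fraction of hypothyroidism cases that are related and held more than 9 weeks. Assuming independence, the total rate is q = 1 − (1 − b)(1 − s·h).

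At b = 10%, the rate that section 14.1 calls acceptable:
- s = 0: q = 0.1000, stopping probability 10.4%.
- s = 0.25: q = 1 − 0.9 × 0.9793 = 0.1186, stopping probability 15.6%.
- s = 0.5: q = 1 − 0.9 × 0.9586 = 0.1372, stopping probability 21.9%.
- s = 1: q = 1 − 0.9 × 0.9173 = 0.1745, stopping probability 36.5%.

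Leaving out the look at patient 20 changes the last three to 14.8%, 20.6% and 34.3%.

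At b = 0, s = 1: q = 0.0827, stopping probability 6.6%. At b = 5%: 2.0% (s = 0), 7.9% (s = 0.5), 18.9% (s = 1).

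**The case against.** There is a good case that this matters less than it seems.

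- **Precedence is partly given.** Section 11.4.2 says that Table 10 governs both drugs for the events it lists. This stands as a pointer to the likely intent. But the sentence is about holding, and neither 10.2.1 nor 11.4.1 refers to it.
- **The rules have limits.** Section 10.2.1 exempts laboratory values that are not clinically significant, so a laboratory-only thyroid change may pass. Section 11.4.1 covers only treatment-related events and allows restart at baseline. Both points stand. Neither releases a symptomatic grade 2 event, and 11.4.1 has no laboratory exception.
- **Patients are not held indefinitely.** A reader might infer open-ended holds. Sections 11.1.1 and 11.4.1 instead end a related hold of more than 9 weeks by taking the patient off the related drug.
- **The texts are not in conflict throughout.** A reader might count every Table 10 and Appendix A difference as a contradiction. Those in Step 2 can be followed together, and section 9.3 introduces Appendix A as recommended guidance.
- **The stopping effect is a worst case and looks backward.** The 36.5% needs every all-grade case to be related and held past the limit, on top of a 10% rate that section 14.1 sets for these events in total. Section 11.3.1 reports one grade 3 case and no discontinuation of pembrolizumab for hypothyroidism. Section 14.1 cites 0% discontinuation for related events in the earlier study of the combination. The boundary covers the first 20 patients, whose response rates section 4.1 already reports, and none is given for the added cohorts. This objection stands in full.
- **Timing.** Section 16.3 speaks in one place of the study as completed. If dosing has ended, an amendment changes no one's treatment.

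**Conclusion.** The contradiction is real and needs no assumption. For grade 2-4 hypothyroidism, grade 2 hyperthyroidism, and resumption at grade 2 under footnote d, the texts can give the same patient opposite dosing instructions. The other differences between Table 10 and Appendix A are matters of alignment.

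The numerical effect is illustrative only. The range of 10.4% to 36.5% rests on an assumed share held past 9 weeks, an assumed 10% rate of other events, independence, and melanoma data that do not give the grade 2 share. Whether a patient stable on replacement stays at grade 2 or higher depends on CTCAE definitions that the protocol does not reproduce. If other events are 0%, the figure is at most 6.6%.

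A reader might infer that the conflict threatens to stop the trial. The documents do not support that, because the only stated boundary belongs to the first 20 patients. For the added cohorts the consequence is inconsistent dosing, exposure and discontinuation, and so safety data that depend on which rule was followed. It should be corrected, but it does not undermine the response endpoint on the evidence available.

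**What to change.** Reconcile section 10.2.1, section 11.4.1, section 11.4.2 with Table 10 and its footnotes, and Appendix A, so that each event and grade has one action for each drug. State in 10.2.1 and 11.4.1 whether Table 10 takes precedence, as 11.4.2 suggests, and use one threshold for resuming. Align the Appendix A entries listed in Step 2 at the same time. Which action is right is for the sponsor.

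The cost is protocol wording in one amendment, with no change to sample size, endpoints or analysis. If dosing has already ended, the study report should say which rule was applied to patients with these events.

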11.0 TOXICITIES/SIDE EFFECTS

Toxicity will be assessed using the NCI CTCAE (version 4.03).

Patients whose treatment is interrupted or permanently discontinued due to an adverse event or clinically significant laboratory value must be followed until resolution or stabilization of the event. As described in section 11.1, a dose delay >9 weeks may require the patient to be discontinued from the study, with exception of patients who undergo surgery.

11.1 Adverse Event Characteristics and Definitions

11.1.1 Definitions of Treatment Related Toxicity Events (TRTE) and decisions based on TRTEs:

Subjects are considered evaluable for feasibility and toxicity assessments if they receive at least one dose of the protocol-assigned dose(s). The treatment related toxicity events that determine feasibility and early-stopping results are defined as those that result in:

- i) study drug(s) discontinuation or
- ii) delay in study drug administration more than 9 weeks from the date of the planned dose (i.e., approximately 12 weeks since the previous dose)

TRTE will be evaluable throughout the study period. The events will only be considered TRTE if judged by the investigator to be related to the administration of talimogene laherparepvec and/or pembrolizumab.

Examples include

- Grade 4 non-hematologic toxicity
- Grade 3 or greater immune-mediated adverse events (except skin).
- Any grade plasmacytoma at or near the injection site or evidence of impaired wound healing at the injection site
- Grade 3 or greater allergic reactions considered at least possibly related to talimogene laherparepvec or pembrolizumab.
- Grade 3 or higher pneumonitis
- Grade 3 non-hematologic toxicity lasting > 3 days despite optimal supportive care
- Any grade 3 or higher non-hematologic laboratory value if:
 - o medical intervention is required, or
 - o the abnormality leads to hospitalization, or
 - o the abnormality persists for > 1 week
- Febrile neutropenia grade 3 or grade 4.
- Thrombocytopenia $< 25 \times 10^9/L$
- Grade 5 toxicity (i.e., death)

The following herpetic events:

- Serious herpetic events such as herpetic encephalitis, encephalomyelitis or disseminated herpetic infection
- For any herpetic events confirmed due to talimogene laherparepvec that require treatment with acyclovir or similar anti-viral agent, treatment with talimogene laherparepvec should be suspended if anti-viral treatment is required with systemic acyclovir or other anti-virals, and if ongoing anti-viral treatment is required, treatment with talimogene laherparepvec should be permanently discontinued

Herpetic events due to wild-type HSV-1 or wild-type HSV-2 which require acyclovir and are not due to talimogene laherparepvec (as confirmed by PCR testing) should not be considered as treatment related toxicity event caused by talimogene laherparepvec. Subjects may be replaced if they are not evaluable for feasibility and treatment related events (e.g., a subject did not receive both study drugs or permanently discontinued talimogene laherparepvec prior to receiving the first dose of pembrolizumab for any reason).

If dosing is delayed by more than 9 weeks from the date of the planned dose (i.e., approximately 12 weeks since the previous dose) due to the occurrence of an adverse event that is considered related to talimogene laherparepvec and/or pembrolizumab, then the subject should be taken off study treatment(s) that the adverse event is deemed to have been related to (see section 11.4.1).

